3.0 Experimental Design

Two controlled, randomized, double-blind clinical trials will be developed and undertaken (one in Brazil and the other in the UK) with an intervention period of 12 weeks.

A questionnaire to screen for the relevant inclusion and exclusion criteria (see section A) will be administered in order to select 80 Brazilian female subjects, aged 20 to 59 years, in each of the two countries. The women selected will be randomly divided into two groups: Placebo Group and Supplemented Group, the latter will receive 600UI UI of vitamin D.

The first clinical trial will run in the UK from October 2016 to March 2017 (autumn-winter) and then the second will run in Brazil from April 2017 to September 2017 (autumn-winter). After the analysis of the effect of vitamin D supplementation compared to placebo, the results obtained in the supplemented group will also be analysed according to the genotypes for SNPs in the VDR gene.

We have chosen 12 weeks (3 months) as the supplementation period as we consider this to be ample time for 25OHD levels to rise (half-life of 25OHD is 3 weeks) and this has been demonstrated to be an effective timeframe for supplementation of vitamin D in previous studies.

We have chosen 600IU to enable the study to be relevant to the new IOM US recommendations for vitamin D, which are currently the reference document used in Brazil, even though the Brazilian nutritional table remains with the daily intake recommendation of 200 IU, which was the IOM recommendation in 1997. Compliance will be checked by compliance interviews during the trial and by empty packaging count.

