We will genotype vitamin D related genes in DNA isolated from the study blood samples, DNA will be extracted and vitamin D polymorphisms will be determined by our genetic labs. These will include known candidate variants (VDR, vitamin D binding protein, CYP2R1, CYP27A1, CYP27B1, and CYP24A1), as well as variants identified by the ongoing genome-wide association analyses on 25OHD. We will construct a genetic risk score based on these polymorphisms. The Genome-wide expression profiling of RNA from leukocytes will focus on 48 participants (each at two sampling time points) that represent equally both groups, encompassing the best and worst supplementation-responders in each group. We will identify the complete spectrum of genes that are, by statistical criteria, either significantly up-or down-regulated (i.e. differentially expressed) between groups. The major comparison will be between the 'good' and 'poor' responders in each group; gene expression prior to supplementation will be compared to after supplementation for each subject analysed.

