3.3.3 Withdrawal

All participants will be notified during the consenting process that they are free to withdraw from the trial at any time, without giving a reason.

Participants will be withdrawn from the trial by the Principal Investigator if:

- 1. The participant develops a medical condition or becomes pregnant either prior to entering the study or during, which may adversely affect the outcome of the study.
- 2. It is clearly demonstrated that the participant is non-compliant completing study activities and the control procedures requested of them.
- 3. A participant suffers an adverse event, which will be reviewed and recorded at each visit and at each phone call, following the immediate discontinuation of the participant during the visit, if necessary.

All data prior to subject withdrawal will be used in analysis; unless the participant specifically requests that their data is not to be used. Withdrawn participants will not be replaced as an anticipated drop-out rate of 20% has been accounted for in the recruitment targets.

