- Anthropometrics and blood pressure measured, and blood sample taken (serum 25OHD levels, 1,25-dihydroxy vitamin D, serum calcium, albumin, parathyroid hormone, C-terminal telopeptide (CTX) ≈25ml) with an additional ≈10 ml for genetic profiling and ≈15 for storage for future measurements of nutritional markers.
- Bioelectrical impedance analysis (BIA) for body composition.
- Dosimeter and 4-day food diary received from participant (sent to participant prior to appointment).

DNA profiling procedure - After 12 weeks RCT

• Selection of 48 participant samples encompassing the best and worst supplementation-responders in each group, subject to previous consent form participant. Vitamin D related genes will be genotyped in DNA isolated from the study blood samples, DNA will be extracted and vitamin D polymorphisms will be determined by University of Surrey's genetic labs.

A trained phlebotomist will take the blood samples required as part of the trial protocol. Medical cover will be available at all times.

Throughout the duration of the trial, the participants will be contacted via telephone on a fortnightly basis to discuss any issues with any adverse event and compliance and to maintain good communication with the participants. (Please see AE reporting form). In the case of a serious adverse event (SAE) this will be recorded (please see SAE reporting form) and we will report it to both the Sponsor (University of Surrey) and the Surrey Ethics Committee.

The final interview will be completed at the final study visit. Participants have also be asked to return any supplements that were missed to confirm compliance.

For University of Surrey participants: A peripheral quantitative computed tomography (pQCT) scan was performed on the participant's non-dominant forearm at the baseline visit, to measure volumetric bone mineral density at the 4% and 66% radial site. This will allow for separate measurements of trabecular vBMD and trabecular area (4% site) and cortical vBMD and cortical area (66% site), as well as strength strain index, a measure of bone strength. pQCT also measures bone geometry alongside bone density. Therefore the muscle cross sectional area can be determined, which is a measure of muscle force, to which bone strength is adapted to. One scan was performed at baseline only and effective exposure doses were between ~1.5-1.8uSv.

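### Adherence is collected but enters no analysis, so the worst responders picked for expression profiling are likely to over-represent women who took fewer doses

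*Combined protocol and SAP*

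**What the plan says.** **Collection.** Section 3.0: "Compliance will be checked by compliance interviews during the trial and by empty packaging count". Section 4.1 adds that "the participants will be contacted via telephone on a fortnightly basis to discuss any issues with any adverse event and compliance", and that women are asked to "return any supplements that were missed to confirm compliance".

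**Use.** The one stated consequence is in Section 3.3.3, where the investigator withdraws a woman if "It is clearly demonstrated that the participant is non-compliant completing study activities and the control procedures requested of them". No number or share of doses is given. The same section states: "All data prior to subject withdrawal will be used in analysis".

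**Selection for the gene work.** Section 3.0 says the expression profiling "will focus on 48 participants (each at two sampling time points) that represent equally both groups", "encompassing the best and worst supplementation-responders in each group". Section 4.1 repeats the selection and adds only that the woman must have consented. Section 3.0 makes good versus poor responders the main comparison, before against after supplementation. Section 1.0 says the aim is to learn whether expression explains who responds well or badly.

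**Analysis.** Section 7.0 lists t or Mann-Whitney tests, ANOVA, correlations, multiple regression and a comparison of three genotype classes. It names no adherence covariate, per-protocol set or adherence sensitivity analysis. Vitamin D intake appears among the correlations, but it is not defined to include study doses and is not tied to the gene work.

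**The concern.** The women are sorted on an outcome that depends on how many doses they took. A woman who took fewer doses will tend to show a smaller 25OHD rise, whatever her biology. She is then more likely to be placed among the poor responders.

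For the expression contrast this matters directly. The second expression sample is taken after supplementation, and fewer doses could plausibly also mean a smaller vitamin-D-driven change in expression. Doses taken would then affect both the sorting and the measurement, and part of a good-versus-poor difference could come from intake. A larger sample would not remove this.

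Inherited genotype is different, because doses taken do not alter it. In the SNP comparisons, uneven adherence mainly adds variation to the response and puts some women in the wrong responder class, which dilutes a true effect. At stake are secondary objective (viii) and hypothesis H5, not the randomised comparison of supplement with placebo.

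**Working it through.** The plan gives no adherence figure, so there is none to reproduce. The check asks how far adherence would differ between best and worst responders under stated assumptions.

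**Inputs from the plan.** 40 women per arm per trial including 20% drop-out (Section 3.1), so 40 × 0.8 = 32 supplemented completers per trial. 48 women are profiled, equally from both groups (Section 3.0), so 24 per group.

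**Assumed.** Groups means countries, and the 24 split evenly into 12 best and 12 worst of 32 supplemented women. Adherence is beta-distributed with mean 85% (SD 15%) or mean 90% (SD 10%).

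**Model 1.** With the mean full-dose rise set to 1:

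response = adherence × (1 + g) + noise

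where g, the true difference between women, has SD 30% to 50%. Other noise is set first at 30% to 50% of the mean rise, then higher. The higher value is suggested by the plan's only effect figure, 0.6 SD (Section 3.1). If the mean rise were 0.6 SD, the between-woman SD would be 1 / 0.6 = 1.67 times the mean rise. Removing g leaves noise of √(1.67² − 0.5²) = 1.59 to √(1.67² − 0.3²) = 1.64, about 160%. This is an illustration only, because 0.6 SD is a detectable difference in 25OHD levels.

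| Adherence, mean (SD) | Other noise | Worst 12: below 80% adherence | Best 12: below 80% adherence | Mean gap, points |
|---|---|---|---|---|
| 85% (15%) | 30–50% | 37–42% | 15–19% | 7–11 |
| 90% (10%) | 30–50% | 19–22% | 8–10% | 3–5 |
| 85% (15%) | about 160% | 32% | 25% | 2.6 |
| 90% (10%) | about 160% | 16–17% | 13% | 1.2 |

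**Model 2, as a check on the form of the model.** A share of women take a fixed fraction of their doses, and everyone's response has residual SD 1. Again 12 best and 12 worst of 32.

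- 20% low takers at half dose, full-dose rise 1.0 SD: low takers are 28% of the worst and 13% of the best, or 12 × 0.28 = 3.4 women against 12 × 0.13 = 1.6.
- Same, with a rise of 2.0 SD: 36% against 7%.
- Mildest case run (10% low takers at 80% of doses, rise 0.6 SD): 11% against 9%.

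Low takers were over-represented among the worst in every scenario run (10% to 30% low takers, 50% or 80% of doses, rise 0.6 to 2.0 SD).

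**Does adjustment work?** Under Model 1, ranking women on the residual from a regression of response on adherence brought the gap to about zero when adherence was measured without error, with no loss of the contrast in true response. With error in the count, part of the gap stays. How much depends on the accuracy of the count.

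**The case against.** The strongest reply is that the effect may be small. Fortnightly calls encourage adherence, and clear non-compliers are withdrawn. A woman who leaves before the final visit has no final 25OHD value and so cannot be ranked. H2 and H3 expect baseline 25OHD and sunlight to influence response, so other variation may swamp adherence. This stands as a limit on size: the low end of the range is about 1 point. It does not remove the direction, because a withdrawal rule without a dose threshold leaves partial takers in the ranking.

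It can also be said that a slope fitted in about 32 women on an imperfect count is unstable, and that reporting adherence by responder group would be enough. That reporting is the minimum. It would show an imbalance after the 48 had been profiled, when reselection is costly.

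Four stronger readings are tempting, and the documents do not support them.

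- **That low intake is certain to be taken for biology.** Adherence is unknown, so likely over-representation is as far as the text goes.
- **That the SNP results are biased.** Genotype does not depend on doses taken. The genotype analysis in Sections 3.0 and 7.0 is also not confined to the 48 extremes.
- **That the packaging count and the returned doses contradict each other.** They are complementary checks on the same quantity. What is missing is one definition that combines them.
- **That the 30-day supply lets one compute how surplus units would distort an adherence score.** Section 4.1 gives one 30-day supply at baseline and mentions re-supply, without its number or size.

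**Conclusion.** The concern holds for the expression contrast. Adherence is recorded, no analysis uses it, and the 48 women are chosen without regard to it. The worst group is therefore likely to contain more partial takers than the best group, and the before/after expression difference may partly reflect doses taken. For genotype the consequence is loss of precision and misclassified responders.

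The size cannot be fixed from the documents. Under the assumed adherence the mean gap runs from about 1 to 11 points: 3 to 11 if other noise is 30% to 50% of the mean rise, and about 1 to 3 if it is near 160%. All these figures rest on the 12-of-32 split. Section 3.0 does not say whether both groups means countries or arms. If it means arms, the point applies to the supplemented half only, since adherence to placebo should not drive a 25OHD rise. The change is worth making because it is cheap and uses data already collected, but it concerns a secondary objective.

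**What to change.** In Sections 3.0 and 7.0, before the 48 are selected:

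1. Define one adherence measure from the packaging and returned-dose counts already collected, with a rule for packs that are not returned.
2. State whether both groups means countries or arms. Among supplemented women, rank response for the 48 on the residual of 25OHD change regressed on adherence.
3. Include adherence as a covariate in the genotype-response analysis.
4. Report adherence for the good and poor responders alongside the expression results.

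The cost is a few sentences and no new data. The downside is that count-based adherence is imperfect: adjustment will remove only part of the imbalance, and a slope from a small group is imprecise. The adherence table in item 4 lets readers judge what remains.

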The data will provide both countries with key data on whether there should be consideration of further revisions to dietary recommendations for vitamin D in adult populations. This study provides good 'value for money' since it draws upon previously collected data in the UK and enables a strong study design to be conducted in the two Countries, simultaneously. The data will be of great interest to the field of Nutritional Sciences by the provision and formulation of data, within a short period of time, examining the interaction of diet and the environment on vitamin D status and its functional consequences. The '**systems level**' approach will enable us to identify differences in gene expression and whether this explains why some individuals are 'good' responders or 'poor' responders to vitamin D supplementation (Wang et al, 2010). This has never been done before in the field, by examining two population groups living in different countries but following identical study designs. Also, to our knowledge, this is the first randomized control trial to analyse the effect of vitamin D supplementation in Brazilian women, either living in the UK or in Brazil.

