3.1 Sample Size and randomisation

A total of 80 subjects (at 90% power) are required for recruitment into the 600 IU vitamin D group vs placebo group for the RCT to be conducted in the UK and a total of 80 subjects (at 90% power) are required for recruitment into the 600 IU vitamin D group vs. placebo group for the RCT to be conducted in Brazil. This will enable us to detect a 0.6 SD size effect at 90% power in serum 25OHD levels between placebo and 600 IU in UK-dwelling Brazilian populations and Brazilians living in Brazil. These study numbers of 40 subjects for the vitamin D group and n 40 for the placebo group includes a 20% drop-out rate factored in.

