4.0 Trial Procedures

4.1 Trial visit activities

During this study the subjects will be asked to visit the Clinical Investigation Unit, FHMS, University of Surrey in the UK or the Research Clinic, Faculty of Nutrition, Federal University of Goias in Brazil, on two occasions, at the beginning of the study for baseline measurements and at the conclusion of the study.

We will examine four to eight fasted subjects per study morning.

Trial visits will last approximately 45-60 minutes each and take place in the morning (7am-11am). Participants will be offered refreshments at the end of their appointment.

Consenting and Screening

If participants wish to be screened for participation in the study, they will receive the Participant Information Sheet and then be checked against the study inclusion and exclusion criteria using the 'Screening Questionnaire' (Section A), to be administered by a member of the D-SOL Research Team by phone or self-reported by email.

Baseline visit

If eligible, participants will be invited for the baseline visit. At this visit, they will first be given time to discuss the Participant Information Sheet and any questions they may have regarding the study.

Informed consent will be discussed and participants will be asked to sign the consent form, and will be offered a copy to keep for themselves.

- Health and Lifestyle questionnaire to be administered by a member of the D-SOL Research Team.
- Anthropometrics and blood pressure measured, and fasted blood sample taken (serum 25OHD levels, 1,25-dihydroxy vitamin D, serum calcium, albumin, parathyroid hormone, C-terminal telopeptide (CTX) ≈25ml) with an additional ≈10 ml for genetic profiling and ≈15 for storage for future measurements of nutritional markers.
- pQCT scan of the non-dominant forearm for UK trial or DEXA scan for Brazil trial.
- Bioelectrical impedance analysis (BIA) for body composition.
- Provision of randomly assigned daily supplement (30 days' supply), food diaries and dosimeter (to be returned via SAE provided) and sunlight exposure diary to be returned at 12 week visit. Follow-up appointment details arranged (including interim visit telephone appointments and for re-supply of supplement).

Final visit

- Final adverse event/compliance interview completed with investigator.
- Daily outdoor exposure diary received from participant and check for consistency at visit.

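### Ranking one 12-week 25OHD change will always yield 'good' and 'poor' responders, and no planned analysis uses placebo to separate varying response from background variation

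*Combined protocol and SAP*

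**What the plan says.** The Background & Rationale (1.0) says the systems-level work will identify differences in gene expression and "whether this explains why some individuals are 'good' responders or 'poor' responders to vitamin D supplementation". Section 3.0 puts this into practice. Profiling "will focus on 48 participants (each at two sampling time points) that represent equally both groups", "encompassing the best and worst supplementation-responders in each group", and "The major comparison will be between the 'good' and 'poor' responders in each group", with expression before and after supplementation compared for each woman. Section 4.1 repeats the rule for the laboratory work after the 12-week trial: "Selection of 48 participant samples encompassing the best and worst supplementation-responders in each group".

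Response is not defined, and no cut-off is given. Women attend "on two occasions, at the beginning of the study for baseline measurements and at the conclusion of the study", so each contributes one change in 25OHD.

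Section 7.0 compares supplemented with placebo by t test or Mann-Whitney. It also plans ANOVA between countries, correlations, multiple regression on blood vitamin D, and ANOVA or Kruskal-Wallis of supplemental response by genotype. Section 3.0 places the genotype analysis in the supplemented group.

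**The concern.** A rank always has a top and a bottom. The rule returns a full set of good and poor responders whether the supplement does nothing, raises 25OHD equally in everyone, or works better in some women than in others. Ranking placebo women in the same way would also give two well-separated groups. One change score cannot show how much of a woman's position is response and how much is background movement. The protocol itself expects sun and diet to affect 25OHD, and follow-up runs through autumn and winter.

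The trial does hold information on background movement, namely the spread of 12-week change on placebo. Section 7.0 uses placebo only for a difference in location. At stake is the explanatory claim in section 1.0: an expression difference between the labelled groups could reflect ordinary 25OHD fluctuation and still be reported as the reason some women respond well to supplementation.

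**Working it through.** The documents give no figure for the separation of the responder groups, so there is none to reproduce.

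**Inputs**
- 48 women profiled in total (3.0 and 4.1).
- "40 subjects for the vitamin D group and n 40 for the placebo group includes a 20% drop-out rate" (3.1), so 40 × (1 − 0.20) = 32 completers per arm per country, and 64 per arm pooled.
- Assumed, not stated: the two groups are countries, each contributing 12 best and 12 worst of its supplemented completers (2 × 24 = 48). Changes are independent and normal.

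**1. Gap from ranking alone.** With zero true variation in response, simulate N changes, sort them, and take the mean of the top k minus the mean of the bottom k.

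| Selection | Mean gap (SD of observed change) |
|---|---|
| 12 v 12 of 32 | 1.97 (95% range 1.48 to 2.51) |
| 12 v 12 of 40 | 2.26 (1.76 to 2.80) |
| 24 v 24 of 64 to 80 | 2.00 to 2.29 |
| 6 v 6 of 32 to 40 | 2.78 to 3.02 |
| 12 v 12 of 64 to 80 | 2.82 to 3.06 |
| Split into halves | about 1.56 |

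No reading brings the gap near zero. The gap in true response is zero in every row.

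**2. How much of the gap is response.** Let f be the share of the variance of change that is true response. If response and background change are independent and normal, the expected true gap is f × observed gap. For 12 v 12 of 32:
- f = 0.10: 0.10 × 1.97 = 0.20 SD; about 63% of labelled women fall on the correct side of the true median (50% is chance).
- f = 0.25: 0.25 × 1.97 = 0.49 SD; about 70%.
- f = 0.50: 0.50 × 1.97 = 0.99 SD; about 80%.

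The documents give no value for f.

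**3. Effect on the gene comparison.** This uses 12 v 12 of 32, identical response in every woman, and a 5% t test per gene. A gene unrelated to change is flagged in 5.2% of simulations. A gene correlated 0.5 (assumed) with background change is flagged in 71%.

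**4. What a comparison of spread can show.** If response and background change are uncorrelated, the ratio of variances (supplement to placebo) is 1/(1 − f): 1.33 for f = 0.25 and 2.00 for f = 0.50. With equal spread, the central 95% of the sample ratio is:
- F(31,31): 0.49 to 2.05.
- F(63,63), pooled: 0.61 to 1.65.

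The chance that a two-sided 95% interval lies wholly above 1 is P(F > upper limit × (1 − f)):

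| | f = 0.25 | f = 0.50 |
|---|---|---|
| 32 per arm | 12% | 47% |
| 64 per arm, pooled | 20% | 78% |

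**5. The assumption behind step 4.** In general, Var(supplement) − Var(placebo) = Var(response) + 2 Cov(response, background change). Set the background SD to 1, the response SD to 0.5 and their correlation to −0.25. The difference is then 0.25 + 2 × (−0.25) × 0.5 × 1 = 0. The spreads are equal although responses truly differ.

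**The case against.** The strongest reply is that the gap is the selection criterion and not a tested result, and that choosing extremes is an ordinary way to use limited RNA. That stands. A reader might infer that ranking itself manufactures gene findings; the 5.2% in step 3 shows that it does not. The randomised supplement-versus-placebo comparison is also untouched.

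A reader might also infer that nothing in the plan examines differences in response. That goes too far. Section 7.0 tests response by genotype, section 3.0 adds a genetic risk score, and dosimeters, sun and food diaries and compliance checks measure several of the background sources. But the genotype test, confined to supplemented women, cannot tell a genotype effect on response from one on background change. No treatment-by-genotype or treatment-by-baseline interaction is planned.

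The figure of 2 SD is conditional. The 12/12 split is not stated, and the meaning of groups is unclear. Section 3.0 says "The women selected will be randomly divided into two groups: Placebo Group and Supplemented Group", whereas H5 in section 2.3 appears to mean the two countries. If arms are meant, placebo women would be ranked and profiled too, which would supply part of the missing contrast, although no analysis is specified that uses it.

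Finally, it is tempting to say that equal spread in the two arms would leave nothing to explain. The documents do not support that. H2 and H3 make response depend on baseline 25OHD and sun exposure, both of which can also affect background change, so the zero-covariance condition is doubtful (step 5). The test is weak as well: with a true share of 25%, the interval would fail to exclude equality 88% of the time per country and 80% pooled.

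**Conclusion.** The point holds as one of interpretation in the genetic sub-study. The labels come from ranking a single change. Under the 12/12-of-32 assumption they imply a gap of about 2 SD of observed change with no variation in response at all, and 1.6 to 3.1 SD under the other readings tried. No planned analysis uses placebo to separate variation in response from background variation, so the plan as written could report correlates of background 25OHD change as supplement-response biology.

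The calculations rest on independent, normal changes and 20% drop-out. The shares in step 2 and the power in step 4 also need response and background change to be uncorrelated. None of this shows that response does not vary. It shows that the plan gives no means of saying how much it does. The change is worth making, but the primary comparison does not depend on it.

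**What to change.** In section 7.0, add a comparison of the spread of 12-week 25OHD change between supplement and placebo (difference in variance, or SD ratio), per country and pooled, with a 95% CI. State that it estimates response variance only if response and background change are uncorrelated.

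In section 3.0, and where section 4.1 repeats the rule:
- Define response, the number taken from each extreme, and whether groups are countries or arms.
- Describe the profiled women as having high and low observed 25OHD change.
- Report the spread estimate beside the expression results, and attribute expression differences to differential response only as far as that estimate supports it.
- Do not treat an interval that includes no difference as a pass/fail gate, or as evidence that response does not vary.

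The cost is wording and one calculation on 25OHD data already planned in both arms, with no extra samples or RNA. The drawback is the imprecision in step 4: the estimate will usually act as a caveat on the responder claim and will seldom settle it.
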